Outcome Measures	
For the burn-in phase, the primary outcome will be time to successful operation of the device (see below for definition), and secondary outcomes include length, type and intensity of use (e.g. use for communication, entertainment, call for help etc), safety, and proof of concept of non-communication features of the device such as wakefulness time monitoring and CAM-ICU capturing.
 
The primary end point of the second step will be number of alive and delirium days while in the ICU and on the ventilator up to 14 days from randomization, or to extubation or ICU discharge, the earliest. Secondary endpoints will include: proportion of patients who were able to operate and use EyeControl, the specific parameters of successful patients compared to those who were unable to operate it; the length and intensity of use; the correlation between the monitoring data and clinical data; and the cognitive and functional long term outcomes as assessed by telephone by the Critical care, Brain Dysfunction and Survivorship (CIBS Center from Vanderbilt University).

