### STEP 2:

**Primary goal:** Measure the time spent alive and non-delirious in the ICU up to 14 days from randomization with EyeControl-based communication compared with the standard of care, in a randomized-controlled fashion.

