As part of its operation, the device captures photographs and video of the patient's eyes (figure 3). In addressing the secondary goal of potential correlation between eye behavior and clinical events, we will explore this possibility by evaluating photographs of the eyes at the times of clinical events (i.e. hypoxia, new onset shock, or new onset sepsis). The device will activate the image data collection only after 50 consecutive frames of eye-in-the-image. This should be a safety index to verify that the device is only recording the eye. It will stop recording immediately when non-eye-in-the-image occurs. Data processing to decide if an eye is in the image is done locally on the device, so eventually only images of eyes should be collected. All external image data processing will be done following deidentification of the data, using the patient code only as an identifier.

Figure 3. Example photographs captured by the EyeControl device.

No randomization or blinding is planned for this step of the study, and no samples are planned to be collected.

---

**STEP 2: MEASURE REDUCTION IN DELIRIUM-FREE AND ALIVE DAYS IN THE ICU WITH EYECONTROL-BASED COMMUNICATION COMPARED WITH THE STANDARD OF CARE.**

The second step will be similar to the operation of the first one, in terms of patient screening and enrolling. The main difference will be the randomization process. Patients will be randomized to use EyeControl for as much as they wish, versus the standard of care. Randomization will be done centrally, and will be stratified to the specific unit, gender and age, race and ethnicity.

The primary goal of the second step will be to measure the time spent alive and non-delirious in the ICU with EyeControl-based communication compared with the standard of care. Delirium will be defined as CAM-ICU positive, starting at day 1 of use (following the day of training), up to 14 days from randomization or ICU discharge, the earliest. However, patients could require moderate to deep sedation following randomization, for example due to new or evolving medical complication. Whenever the RASS is below (-1), CAM-ICU will not be measured, and will be charted as undetermined. Therefore, only days in which the patient will be CAM-ICU positive, will be counted towards the primary outcome. CAM-ICU positive days prior to randomization will not be counted towards the primary outcome.

[figure not shown]
The secondary outcomes will include the following:

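### The Step 2 primary endpoint is defined inconsistently: what is counted, when counting stops and when it starts differ between sections, and the SAP does not settle it

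*Combined protocol and SAP*

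**What the plan says.** **Quantity.** Study Purpose (Step 2, primary goal) reads "Measure the time spent alive and non-delirious in the ICU up to 14 days from randomization". The goal sentence under Study Design and Methods, Step 2, agrees: "The primary goal of the second step will be to measure the time spent alive and non-delirious in the ICU with EyeControl-based communication". The Statistical Analysis Plan (Step 2) names the same quantity as the primary outcome and repeats it for the stratified Mann-Whitney test and the median regression.

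Three places differ. The Step 2 design text, after defining delirium as a positive CAM-ICU, says "Whenever the RASS is below (-1), CAM-ICU will not be measured, and will be charted as undetermined" and continues "Therefore, only days in which the patient will be CAM-ICU positive, will be counted towards the primary outcome". Its next sentence is "CAM-ICU positive days prior to randomization will not be counted towards the primary outcome". The Synopsis (Outcome Measures) has "number of alive and delirium days while in the ICU and on the ventilator up to 14 days from randomization, or to extubation"; leaving the ICU also ends the count. The Step 2 heading is "MEASURE REDUCTION IN DELIRIUM-FREE AND ALIVE DAYS IN THE ICU", which runs against the intended benefit.

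**Start and stop.** The Step 2 design text counts "starting at day 1 of use (following the day of training), up to 14 days from randomization or ICU discharge, the earliest". The Synopsis also stops at extubation.

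**Planning basis.** Sample Size takes 6.8 ± 5.2 delirium/coma-free days over the first 14 days of admission, words the target as 2 fewer days delirious, and arrives at 248 patients (124 per arm).

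**The concern.** This is the primary comparison of the randomized step. Two analysts who follow the documents faithfully could derive different primary variables: one where more days are better, another where fewer are better, with different last days and possibly different first days by arm. If this stays open until data are available, the choice could be made with results in view. It also leaves unclear which quantity the planning SD and the 2-day target should describe.

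**Working it through.** **1. The plan's own figure.** Inputs from Sample Size: difference 2 days, SD 5.2, power 80%, alpha 0.05 (taken as two-sided), minimal efficiency of the Mann-Whitney test. The efficiency value is not printed; 0.864 is the standard lower bound.

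- Normal approximation: n per arm = 2 × 5.2² × (1.960 + 0.842)² / 2² = 106.1. Divided by 0.864 this is 122.8, so 123 per arm and 246 in total.
- t-based: 107.09 / 0.864 = 123.9, so 124 per arm and 248 in total. This matches.
- Detectable standardized difference at 124 per arm: 2.802 × √(2 / (124 × 0.864)) = 0.383, against the stated 0.38.

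The arithmetic is correct. The SD describes delirium/coma-free days from admission, whereas every version of the endpoint counts after randomization and in the ICU.

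**2. How the two counts relate.** For one patient let T be countable ICU days alive, P CAM-positive days, U undetermined days and N clear days. Then N = T − P − U. For differences in means between arms, ΔN = ΔT − ΔP − ΔU. If ΔT = ΔU = 0, then ΔN = −ΔP and the counts are mirror images. If ICU time, deaths or undetermined days also differ, they need not be.

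**3. Constructed patients, ICU-discharge stop, no assumed rates.**

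| Patient | Non-delirious days (more is better) | CAM-positive days (fewer is better) |
|---|---|---|
| A: leaves the ICU clear after day 3 | 3 | 0 |
| B: 14 ICU days, 5 CAM-positive, 9 clear | 14 − 5 = 9 | 5 |
| C: never delirious, dies after day 2 | 2 | 0 |
| D: 14 ICU days, 10 undetermined, 4 clear | 4 if undetermined days are left out, 14 if they count as non-delirious | 0 |

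B beats A on the first count and loses to A on the second. C ties for best on the second count.

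**4. Stop.** Take a patient who is CAM-positive on days 1 to 6, extubated after day 2, clear on days 7 and 8, and discharged from the ICU after day 8. With the Step 2 stop the scores are 6 positive and 2 non-delirious days. With the Synopsis stop they are 2 and 0.

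**5. Start.** Number days from randomization as day 0. If training falls on day k, the device patient's window is days k + 1 to 14, at most 14 − k days. No start is given for controls. If theirs were day 1, they would have up to 14 days. With k = 1 the maximum is 13 against 14, and with k = 2 it is 12 against 14. A shorter window can only lower a count, which works against the device on non-delirious days and in its favour on CAM-positive days. The Synopsis lists the proportion able to operate the device as a secondary endpoint, so some device patients may also lack a clear first day of use.

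**6. What the SAP adds.** It is consistent on the quantity but states no 14-day limit, start, stop, or score for undetermined days or for days after death or ICU discharge.

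**The case against.** The best defence is that the disputed Step 2 sentence classifies days and does not define a second endpoint. The passage opens by equating delirium with a positive CAM-ICU, and the sentence follows directly from the rule on undetermined days. It may mean only that undetermined days are not delirium days. That reading fits the goal sentence, Study Purpose and the SAP, and the sentence on days before randomization can be read the same way. The Synopsis phrase may simply have lost a word, and the Step 2 heading may be a slip.

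Much of this stands. The reading is plausible, and under it patient D scores 14, so it cannot be said flatly that undetermined days have no rule. But it departs from the sentence's literal words. It also credits days of moderate or deep sedation as non-delirious, while the planning figure counts days free of both delirium and coma. The stop and start conflicts remain under either reading.

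A reader might go further and infer that the trial could favour the wrong arm. The documents do not support that as a prediction. The hypothesis concerns delirium, and if delirium alone differs the versions agree in direction. No passage says that the device changes ventilation time, ICU stay, sedation or mortality; the background reports only that delirium correlates with longer stay and death. Any size put on such a reversal would rest on assumed rates.

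**Conclusion.** The inconsistency holds on three points: the counted quantity, the stop event, and a start that exists in one arm only. The SAP settles the quantity in its own text but none of the rest, and nothing says that it overrides the design section. The primary variable therefore needs correction before Step 2 is analysed.

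The size is shown by constructed patients: the ranking of two patients can reverse (9 and 5 against 3 and 0), one patient's score can move from 4 to 14 on the undetermined-day rule, and one patient's CAM-positive count from 6 to 2 on the stop rule. These show that the definitions are not interchangeable. They do not estimate bias or lost power in this trial, for which the documents give no rates.

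Two stronger inferences are not supported. The figure of 248 is not miscalculated; the open question is whether an SD of 5.2 transfers to the endpoint finally chosen. Nor is an in-ICU endpoint wrong in itself: it is defensible once it is stated consistently, with early discharge and death given explicit scores.

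**What to change.** Write one definition and use it in the Synopsis, Study Purpose, the Step 2 heading and text, and the SAP. It should state:

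- one counted quantity and which direction is better; if the non-delirious endpoint of Study Purpose and the SAP is kept, correct the two Step 2 sentences on CAM-positive days, the Step 2 heading and the Synopsis wording;
- a start anchored to randomization and identical in both arms, whether or not a patient has been trained on the device;
- one stop event, with extubation either included everywhere or removed everywhere;
- the 14-day window, which the SAP lacks;
- an explicit score for undetermined days and for days after death or ICU discharge.

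Then say whether the SD of 5.2 and the 2-day target apply to that endpoint. If they do not, justify new values and restate the power of 248.

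The cost is small: wording in four sections and a short sample-size check. CAM-ICU, RASS, ICU discharge and mortality are already part of the planned data, so no new assessment is needed for an in-ICU endpoint.

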## SCHEDULE OF EVENTS

SCHEDULE OF EVENTS	SCREEN ENROLL (DAY 0)	ICU admission	DAY 180
Procedure			
Eligibility Verification	X		
Informed Consent	X		
Lead diagnosis for ICU admission	X		
Physiologic Data (Vitals, GCS, etc)	X	X	
Neuroimaging (if available)	X	X	
Demographics	X		
Medical History	X		
Laboratory Results	X	X	
CAM-ICU q12h	X	X	
Discharge Data		X	
Clinical Endpoint Monitoring	X	X	X
General Questionnaire re: communication in ICU		X	X
Follow-up Assessments			
Neurocognitive Battery			X

## TABLE OF ABBREVIATIONS

AE	Adverse Event
APP	Advanced Practice Provider
ARICU	Acute Respiratory Intensive Care Unit
CAM-ICU	Confusion Assessment Method in Intensive Care Unit
CCU	Cardiac Intensive Care Unit
CRF	Case Report Form
CTS-ICU	Cardiothoracic surgery Intensive Care Unit
EMR	Electronic medical record
ICU	Intensive Care Unit
IRB	Institutional Review Board
LAR	Legally Authorized Representative
LOC	Level of Consciousness
LOS	Length of Stay
MD	Medical Doctor
MICU	Medical Intensive Care Unit
NeuroICU	Neuroscience Intensive Care Unit
RASS	Richmond Agitation Sedation Score
RN	Registered Nurse
SICU	Surgical Intensive Care Unit

## BACKGROUND AND SIGNIFICANCE

Critically ill patients, who are mechanically ventilated, suffer not only from their acute, potentially devastating illness, but also from the lack of ability to communicate in an effective manner. On top of the mechanical change in air flow, communication challenges result from sedation, neurological injuries (primary brain injury or secondary encephalopathy), and delirium. Lack of communication can lead to increased frustration, anxiety, confusion and delirium and overall psychological stress, and could continue to the development of post- traumatic stress disorder (PTSD). On top of the subjective discomfort, the inability to communicate in an effective manner may impair medical care—for example, by failure to assess symptoms such as pain or breathing discomfort. In order to solve these difficulties, a new, wearable, eye-tracking communication device was developed (EyeControl).

## STUDY RATIONALE

### COMMUNICATION IN THE CRITICALLY ILL

Critically ill patients, who are mechanically ventilated, suffer not only from their acute, potentially devastating illness, but also from the lack of ability to communicate in an effective manner. This is the direct result of the orotracheal tube or tracheostomy required for the mechanical ventilation, which does not allow speech to be produced. On top of the mechanical change in air flow, communication challenges result from sedation, neurological injuries (primary brain injury or secondary encephalopathy), and delirium.

Lack of communication can lead to increased frustration (Guttermson et al., 2014), anxiety, and overall psychological stress (Carruthers et al., 2017) and could continue to the development of post-traumatic stress disorder (PTSD) (Wade et al., 2012). On top of the subjective discomfort, the inability to communicate in an effective manner may impair medical care—for example, by failure to assess symptoms such as pain (Chanques et al., 2014) or breathing discomfort (Binks et al., 2017) by behavioral cues only.

### DELIRIUM IN THE ICU

One of the dreaded complications in critically ill patients is delirium. Delirium is an acute form of encephalopathy, or brain dysfunction, that is manifested by waxing and waning changes in cognitive abilities during acute illness. Delirium is diagnosed in 48-83% of critically ill patients (Girard et al., 2018, Ely et al. 2001), and is linked to increased mortality (Ely et al., 2004). Several risk factors associated with delirium include older age, prior neurological injuries or neurodegenerative disorders, as well as the acuity of illness and admission in the ICU (Ely et al., 2001; Oldham et al., 2018). Disorganized sleep is also linked to higher risk of delirium (Dres et al., 2019; Marra et al., 2019a). Delirium is strongly correlated with worse outcomes, including longer length of stay in the ICU and the hospital, and increased mortality (Marra et al., 2019b). Treatment for delirium includes pharmacological (mostly anti-psychotic medications) and non-pharmacological interventions (Marra et al., 2019). Non-pharmacological interventions to prevent and treat delirium include early mobilization, frequent reorientation, etc. (Martínez et al., 2017). Recently, a large randomized controlled trial failed to show benefit for pharmacological interventions to treat and prevent delirium, leaving non-pharmacological interventions as the main treatment option for now (Girard et al., 2018). Lack of effective communication not only could impair such non-pharmacological interventions but limit the diagnosis of delirium in the first place (Rowley-Conwy, 2018). However, from a diagnostic stand point, others have shown a valid method to diagnose delirium even in mechanically ventilated patients (Ely et al., 2001).

[figure not shown]
## HOW MANY PATIENTS WOULD BENEFIT FROM A COMMUNICATION DEVICE?

[figure not shown]
On average, across the U.S., 39.5% of patients in the ICU at any given hour require mechanical ventilation (Wunsch et al., 2013). Estimating the number of patients who have an unmet communication need is difficult. Not all patients who are mechanically ventilated could communicate, even with assistance. For example, a patient who suffered a large stroke in the dominant hemisphere will suffer from aphasia and may not be able to communicate efficiently, with or without being ventilated. Similarly, in many critically ill patients, there is a need for continuous sedation, which limits the patient's ability to communicate.

Happ et al. (2015) estimated the number of patients who are mechanically ventilated and potentially could communicate. They found that 53.9% of patients who were mechanically ventilated for at least 48 hours were awake and following commands for at least 12 hours (one nursing shift).

Analyzing the data from the years 2016 to 2018 at EUH, there are, on average,  $469 \pm 37$  admissions to all ICUs per month. In order to identify the potential study population, we examined what proportion of patients were ventilated for at least two, three, or five days. We further calculated the duration of ventilator days for these patients, rate of tracheostomy, and the proportion of patients who had at least two days in which their RASS was documented as -1 to 1, suggesting that they were awake and cooperative enough to engage with a communication device.

We found that 27.8% of admissions to the ICU were intubated for at least 48 hours, while 18.9% were intubated for at least three days and 12.6% were intubated for at least five days. The mean number of ventilator days for patients ventilated for at least two days was 8.6, and 11.6 and 16.2 for patients ventilated for at least three and five days, respectively. Given the high mean number of ventilation days for the patients who are ventilated for at least two days, it seemed reasonable to further analyze this group as a the inclusion criterion. We further found that nearly 25% of the patients ventilated for at least two days had recorded RASS of -1 to 1 for at least two days, suggesting a window in which these patients could potentially communicate (see Figure 1A for breakdown by units). It was also found that 17.9% of patients ventilated for at least two days ended up being ventilated long- term, requiring a tracheostomy (see Figure 1B for breakdown by units). We hypothesize that this group, those who will need to be on the ventilator for a long period of time, will be the patient population that will mostly benefit from a wearable, eye-tracking-based communication device. At Emory, by this retrospective analysis of the past three years, we are estimated to screen about 130 patients per month who are ventilated for at least two days.

**Figure 1:** Breakdown of patients by units who are ventilated for at least two days and have RASS between -1 to 1 for at least two days (A) and patients who ended up requiring tracheostomy (B).

#### EYE-CONTROL DEVICE

Currently, the solutions for communication deficits in mechanically ventilated patients are mainly using yes/no communication, attempting to write, and communication boards that allow people to point at defined pictures or letters (Khalaila et al., 2011). Recently, technological advancements led to incorporation of more sophisticated communication devices, proving the feasibility of an eye-tracking approach, for example (Carruthers et al., 2017).

The EyeControl is a new, wearable, eye-tracking device (Figure 2) that facilitates communication by means of internal feedback to the patients with a bone-conducting speaker. In this way, the device can ask the patient what he or she wants to say, and the patient replies by eye gestures such as blinking or moving the eyes in a certain direction. This approach eliminates the need for calibration, as most eye-tracking devices that use a screen require, and is relatively easy to operate. It is currently being tested in general ICU-based settings in Tel Aviv, Israel, where the company reports nearly 100% success in teaching patients to use the device within minutes.

**Figure 2:** The EyeControl device.

This device has other potential advantages that could be utilized in the critical care settings. It could be used as a monitor; for example, it could record times that the patient has her or his eyes open as a marker for wakefulness (it could be an important indirect marker for quality and length of sleep); it could use its communication with the patient to assess for delirium (using known basic questionnaires such as the CAM-ICU); it could assess, to some extent, the ability to follow commands with blinking and eye movements. The device could be part of the non-pharmacological interventions to prevent and treat delirium. For example, it could state the day, time, and location to the patients every few hours.

The risk associated with the device seems very low. It is external, wearable, and could be easily removed with any signs of discomfort. No significant side effect was recorded from using this device according to the manufacturer.

## STUDY PURPOSE

To determine the safety, tolerability, and ease of use of the EyeControl device and determine impact on communication and delirium in critically ill, ventilated patients in the intensive care unit.

### STEP 1:

**Primary Goal:** Assess the safety, tolerability, and ease of use of the EyeControl device. The outcome measure for this goal will be the time of training required for a patients to successfully execute two tasks using the device: call for help and choose a predefined sentence for the device to say three times straight.

#### Secondary Goals:

1. Assess the proportion of mechanically ventilated, critically ill patients, with or without primary neurological injury, who could benefit and operate an eye-movement-tracking device as a means of communication.
2. Assess the type and length of the use done by the patient. For example, we will monitor how long a patient wears the device, uses it, and for what purpose (communication, call for help or entertainment).
3. Assess the EyeControl device as a diagnostic/monitoring tool for delirium in comparison to the bedside nurse assessment. Specifically, the device will record times of wakefulness for each 24h period of time, and will test for delirium using CAM-ICU. The later will be correlated with a live, verbal assessment done by a study team member.
4. Assess patient proficiency in device operation through daily orientation questionnaire.
5. Assess the change in level of frustration and discomfort patients and families feel in relation to communication with and without the device. These will be assessed by a questionnaire given to patients and families near their discharge.
6. Explore possible correlation between eye movements and clinical events by evaluating photographs of the eyes at the times of these events.

